#### **Month 18-21:**

For a subset of 250 patients with an inappropriate laboratory test, a review of data extracted from the EHR will be organised to identify all downstream activities. These patients will also be interviewed by telephone to identify downstream activities not recorded in the EHR. See 8.9.3 for more detail on this assessment.

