We will not recruit patients, but will include all patient data from those patients where laboratory test orders were made for one or more of the 17 study indications. All included patients will be followed for a period of six months, and in case their physician indicates that a potentially missed diagnosis has been made in that year, a review of data extracted from the EHR and patient interviews will be performed to confirm the missed diagnosis.

For a subset of 250 patients with an inappropriate test, data extracted from the EHR will be reviewed to identify the downstream or cascade activities resulting from this test (see section 8.9.3 for detailed information).

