### 8.9.3 Downstream activities

We will include one exploratory outcome in our study, this being the effect of evidence-based order sets on downstream or cascade activities. Literature suggests that improving appropriateness of laboratory testing has an effect which is much larger than simply on the amount of tests ordered. It reduces the amount of unnecessary testing due to deviant tests of unknown significance. This effect on over-diagnosis and downstream or cascade activities is often referred to as the 'Ulysses effect' (Rang 1972). Some exploratory studies have shown that the Ulysses effect may not be as important in primary care as literature suggests, but good evidence remains lacking. Evaluating these downstream or cascade effects is a resource-intensive work as this can only be done through manual review of data extracted from the EHR and completed with direct patient interviews. In a subset of 250 laboratory panels, we will review the corresponding patient charts and identify all those activities originating directly from the results of the ordered laboratory tests. We will use the methods by Houben et al (Houben 2010) as a guide to identify those laboratory panels that could potentially lead to downstream or cascade activities. We will focus on inappropriate tests in both the control and intervention arm to evaluate the extent of downstream activities and compare the difference in downstream or cascade activities between abnormal and normal results. This outcome will be measured 6 months after the initial laboratory test order. This data will also be used in any cost-effectiveness analysis resulting from this trial.

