This table has an identical structure to the TU_KCELABGP_LAB and TU_KCELABGP_LAB_LAB_TST tables, but contains data on the patients for which cascade tests were ordered.

6.1.2.KCELABGP_GP

The KCELABGP_GP database contains information collected from the electronic health records (EHR) of the physicians on the patients included in the study. This data was collected directly from within the EHR through an electronic clinical report form (eCRF), called an eForm. Each row coincides with an item on this eForm.

TU_KCELABGP_GP

This table contains data on each eForm. Each row corresponds to an individual eForm and contains information on the patient such as sex, date of birth, date of death (if applicable), number of new diagnoses recorded through the eForm, date of the laboratory test panel, information on why the test was ordered and information on any cascade activities.

Each row in this table represents a unique eForm, so for a single patient there may be multiple rows, as for each included laboratory panel a corresponding eForm was collected. Each row has a unique identification key, named 'TXT_WRKFLOW_IDN', through which all data in this database can be linked to an individual eForm.

TU_KCELABGP_GP_DIAG

This table contains data on the new diagnoses recorded through the eForm. Each row represents a unique diagnosis and includes information on the date of the new diagnosis, information on whether the physician considered the diagnosis as related to the laboratory test (either to the indication of the laboratory test order or to the result of one of the laboratory tests in the panel), whether the new diagnosis was diagnosed timely, the name of the new diagnosis and International Classification of Primary Care (ICPC-2) or International Classification of Diseases (ICD-10) codes.

TU_KCELABGP_GP_DWNSTRM_INV

This table contains data on all the downstream investigations recorded through the eForms. Each row represents a unique downstream investigation and includes information on the patient, the type of investigation and free text additions registered by the physician.

TU_KCELABGP_GP_DOWNSTRM_REF

This table contains information on the downstream referrals recorded in the eForm. Each row represents a unique downstream referral and includes information on the patient and on the specialty of the specialist or other healthcare professional to whom was referred.

6.1.3.KCELABGP_PAT

TU_KCELABGP_PAT

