10.2.3. Exploratory outcome analysis

The total number of cascades per patient will be analysed using the same methodology as for the total number of tests (test volume, see supra).

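### The protocol's only cascade sample is selected on having an inappropriate test, and the SAP does not say whether the arms are compared within it

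*Protocol*

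**What the plan says.** **Sample.** Protocol 8.1 introduces the cascade review with "For a subset of 250 patients with an inappropriate test". Protocol 8.8 (Month 18-21) repeats it: "For a subset of 250 patients with an inappropriate laboratory test". Protocol 8.9.3 gives a different unit: "In a subset of 250 laboratory panels, we will review the corresponding patient charts". No section says how the 250 are divided between the arms or drawn within them, and the number has no derivation.

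**Aim.** Protocol 8.9.3 describes the outcome as "this being the effect of evidence-based order sets on downstream or cascade activities". It adds: "We will focus on inappropriate tests in both the control and intervention arm". It also names a second contrast, abnormal against normal results, and says that the data will feed any cost-effectiveness analysis.

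**Analysis.** Protocol 9.3.4.1 and SAP 10.2.3 use the same sentence: "The total number of cascades per patient will be analysed using the same methodology as for the total number of tests". The test-volume method is a count GEE with allocated group as a factor, reported as a ratio between groups (Protocol 9.3.3.2, SAP 10.2.2).

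**Data.** The SAP never mentions the 250. In SAP 6.1.2 the eForm, one per included panel, holds "information on why the test was ordered and information on any cascade activities". SAP 6.1.3 lists downstream tables from the patient interviews as well.

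**The concern.** The order sets are meant to reduce inappropriate tests. A patient spared every inappropriate test can have no cascade from one, and that zero is part of the benefit. A sample restricted to patients with an inappropriate test leaves those zeros out, and leaves out more of them in the intervention arm. The remaining patients are also no longer comparable by randomisation, because membership depends on something that the intervention changes.

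If the group-factor model were run on the 250, its ratio would not estimate the effect of the order sets. Protocol 2 counts downstream effects among what is needed to evaluate cost-effectiveness fully, so a distorted ratio could carry into that work.

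**Working it through.** **Step 1: the plan's own figures.** The 250 cannot be reproduced, as no calculation is given. The rates used below are those of Protocol 9.1.1, whose sample size does reproduce. Per arm, n = [1.96·√(2·0.75·0.25) + 0.8416·√(0.21 + 0.16)]² / 0.10² = 293.15, or 586.3 tests in total against the stated 586. The design effect with ICC 0.2 is 1.8 × 5.556 × 1.2465 = 12.465, giving 7305 tests, as stated.

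**Step 2: inputs.**
- Inappropriate tests: 30% in control, 20% with order sets (Protocol 3.1, 9.1.1).
- Tests per patient: 5 (Protocol 9.1), or about 14, since Protocol 4 reports 14.2 to 14.61 per panel at the laboratories.
- Correlation between tests in one patient: 0 (independent), or 0.2 (Protocol 9.1.1).
- Assumed: the same cascade rate per inappropriate test in both arms, the same number of tests per patient in both arms, and selection on at least one inappropriate test.

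**Step 3: formula.** With m tests and proportion q inappropriate, expected cascades per patient are proportional to m·q. Among patients with at least one inappropriate test they are proportional to m·q / P, where P is the probability of at least one. Hence

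ratio in selected patients = (0.20/0.30) × P(control) / P(intervention).

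The ratio in all patients is 0.20/0.30 = 0.667. With independent tests P = 1 − (1 − q)^m. With ICC 0.2, P comes from a beta-binomial with parameters 4q and 4(1 − q), since 1/0.2 − 1 = 4.

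Worked case, 5 independent tests: P(control) = 1 − 0.7⁵ = 0.832 and P(intervention) = 1 − 0.8⁵ = 0.672. The ratio is 0.667 × 0.832/0.672 = 0.825.

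| Tests | ICC | P control | P intervention | Ratio, selected | Share of log effect kept |
|---|---|---|---|---|---|
| 5 | 0 | 0.832 | 0.672 | 0.825 | 47% |
| 5 | 0.2 | 0.700 | 0.536 | 0.871 | 34% |
| 14 | 0 | 0.993 | 0.956 | 0.693 | 91% |
| 14 | 0.2 | 0.880 | 0.745 | 0.788 | 59% |

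**Step 4: higher baseline.** Protocol 5.2 cites 38 to 60% inappropriate tests for five frequent indications. With a fall from 50% to 40%, the ratio in all patients is 0.800. In selected patients it is 0.840 or 0.876 with 5 tests (ICC 0 or 0.2), and 0.801 or 0.827 with 14.

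**Step 5: counting per inappropriate test.** If each count is divided by inappropriate tests rather than by patients, equal rates give a ratio of 1.00 whatever the intervention achieves.

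**Step 6: what 250 patients could show.** Assume 125 per arm, 5 independent tests, no clustering, and λ cascades per inappropriate test. Without selection, SE = √(1/(125·1.5λ) + 1/(125·1.0λ)) and power = Φ(|ln 0.667|/SE − 1.96). With selection, 1.5 and 1.0 are replaced by 1.5/0.832 and 1.0/0.672, and 0.667 by 0.825.

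| λ (assumed) | Power, no selection | Power, selected |
|---|---|---|
| 0.05 | 12% | 6% |
| 0.1 | 20% | 9% |
| 0.2 | 35% | 14% |
| 0.5 | 70% | 28% |

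**The case against.** The text on the 250 does not itself announce an arm comparison. Protocol 8.8 only has activities identified in them, and the one contrast that Protocol 8.9.3 spells out is abnormal against normal results, which this selection suits. The SAP is the later document. It analyses cascades per patient, mentions no subset, describes a cascade field on the form for every included panel, and in 10.3 excludes only patients without data. That can be read as an analysis of everyone with an eForm. Its exploratory objective (2.2.4) restricts which cascades count, not which patients are in the denominator.

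Much of this stands. A reader might infer that the trial is committed to a biased comparison. The documents do not go that far: the SAP leaves the analysis set undefined. But it presents itself as elaborating the protocol, it does not withdraw the subset, and the protocol applies a between-arm model without defining any other cascade sample.

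A reader might also infer that the selection hides the benefit entirely. That would require counting per inappropriate test, or equal cascades per selected patient in both arms. The planned measure is per patient, and order sets can also lower the number of inappropriate tests in patients who still have one. SAP 10.2.1 counts every requested test, so the results for about 14 tests may be the closer guide, and there 59 to 91% of the log effect remains.

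Nor is the direction certain. Weakening follows from the equal-rate assumption. Differences in case mix between the selected groups could move the ratio either way.

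**Conclusion.** The point holds as a mismatch between aim, sample and model. The aim and model are between-arm, the only cascade sample that the protocol defines is selected on a post-randomisation variable tied to the primary outcome, and the SAP does not settle which patients are analysed. Under the stated assumptions, a ratio of 0.667 would appear as about 0.83 to 0.87 with 5 tests per patient, or about 0.69 to 0.79 with 14. The loss of comparability between arms needs none of those assumptions.

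The consequences are limited. The outcome is exploratory, and the economic evaluation (Protocol 9.10) is optional, conditional on effectiveness, and starts from cost per appropriate test. This is a cheap improvement and does not threaten the trial's main conclusions.

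**What to change.** In SAP 10.2.3, state that the between-arm cascade analysis includes all included patients with a linked eForm, whatever the appropriateness of their tests, and that patients without a cascade count as zero. Label the 250-patient review as descriptive: the extent of cascades after inappropriate tests, and abnormal against normal results. Say whether its unit is the patient or the panel.

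If chart review with interview is wanted for the arm comparison, draw the 250 at random within each arm without regard to appropriateness. Step 6 shows that this would still have low power unless cascades are frequent.

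The first option changes wording only, since the eForm already holds cascade information, but three drawbacks should be stated with the result:
- The reporting physicians know their allocation (Protocol 8.3.1).
- About 15% of patients have no eForm (SAP 10.3).
- Capture may be less complete than chart review with interview, which Protocol 8.9.3 regards as the only way to evaluate cascades.

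Interview-reported cascades should stay out of the main arm count unless the interviewed patients were sampled in the same way in both arms.

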#### **Month 24:**

The collaborating laboratories will provide the research facility with data on total laboratory test ordering volume for the 3 month study period. They will also provide data of the laboratory test ordering volume in the 9 months after the study period for the intervention group. These data will be used to evaluate sustainability of the intervention effects for the intervention arm.

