### 3.3.3 Exploratory endpoints/outcomes

We will attempt to assess the effect of our intervention on the downstream activities arising from abnormal results of inappropriate tests. A full description of this assessment can be found under 8.9.3.

Objectives	Outcome Measures	Timepoint(s) of evaluation of this outcome measure (if applicable)

Primary Objective:
 
 
To compare the effect of evidence-based order sets versus control on the proportion of appropriate laboratory tests ordered by primary care physicians
 
	
Primary Objective:
 
 
We will evaluate the effect of 17 order sets on the appropriateness of laboratory tests. This will be measured for all tests collected from 300 physicians over a period of 3 months
 
	
Primary Objective:
 
 
Data collection from the LIS 3 months after the start of the study
 

Secondary Objectives:
 
 
To compare the effect of evidence-based order sets versus control on diagnostic error by primary care physicians
 
To compare the effect of evidence-based order sets versus control on the amount of laboratory tests ordered by primary care physicians
 
	
Secondary Objectives:
 
 
We will evaluate the effect of 17 order sets on diagnostic error
 
We will compare volume of laboratory tests for each indication. We will also continue to monitor test volume after the intervention period in both the intervention and control arms
 
	
Secondary Objectives:
 
 
We will continuously survey study physicians during the study. Responses by physicians will be verified through review of data extracted from the HER
 
We will extract laboratory test volume data from the LIS at 6 months and 12 months after the start of the study
 

**Table 1:** Summary of primary and secondary objectives, outcomes and time points of evaluation

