## 6 TRIAL DESIGN

Our trial will be designed as a cluster randomised controlled trial and powered as a superiority trial for our primary outcome. **For the secondary outcome, the trial will seek to establish non-inferiority. The trial will have sufficient statistical power for both outcomes and will include of a three month intervention period and a six month follow-up period.**

**Six months after the end of the intervention period**, all participants will receive our intervention and we will continue to measure appropriateness and volume of testing in a prospective observational design in the original intervention group as a measure of sustainability.

We will randomize participating PCPs to the intervention or to a control group. The unit of allocation is the PCP. This means that all physicians in the same practice will be allocated to the same intervention and that either all or no physicians in the PCP will be included in the trial. All patients cared for by the same primary care practice will be exposed to the same intervention. In this description, we assume the recruitment of 300 physicians. In the case where less physicians are recruited, we will use an adaptive design as described in [Appendix 3](#).

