### 6.1 Cluster randomised controlled design

During a period of nine months, 150 intervention physicians will be exposed to our intervention and 150 control physicians will not. After these nine months, all physicians will be exposed to our intervention. Three months are sufficient to measure the effect of our intervention on a significant amount of patient contacts and laboratory test orders, and data on appropriateness will be collected at three months. At nine months, and after the data collection for diagnostic error, all study physicians will receive our intervention. Figure 10 illustrates the flow of the study with a sample of at least 300 physicians.

[figure not shown]

Figure 10: Flow of trial for appropriateness for sample of 300 physicians.

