### 8.9.2 Sustainability of implementation impact

Six months after the end of the intervention period, all participants will receive our intervention. This cross-over is motivated by two reasons: first, the laboratories perceive this intervention as a service to their customers. They cannot consent to withholding a substantial portion of their clients to this service. Moreover, prolonging the study period may demotivate participants in the control group. Second, we would like to measure the sustainability of our intervention over time in the intervention arm. **The cross-over will allow us to lengthen the follow-up period for the physicians in the initial intervention arm.**

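### Protocol 8.8 requests later test volume for the intervention arm only, contradicting Table 1; if followed, sustainability has no concurrent control, although one exists for six more months

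*Protocol*

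**What the plan says.** Under Month 24, Protocol 8.8 has the laboratories supply total volume for the three-month study period, with no arm named, and then "laboratory test ordering volume in the 9 months after the study period for the intervention group". The purpose is stated next: "These data will be used to evaluate sustainability of the intervention effects for the intervention arm".

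Protocol Table 1 (section 3.3.3) says otherwise: "We will also continue to monitor test volume after the intervention period in both the intervention and control arms". It gives the timing as "We will extract laboratory test volume data from the LIS at 6 months and 12 months after the start of the study".

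On exposure, Protocol 6.1 says "During a period of nine months, 150 intervention physicians will be exposed to our intervention and 150 control physicians will not", and 8.9.2 says "Six months after the end of the intervention period, all participants will receive our intervention". Protocol 6 describes the follow-up from that point as a "prospective observational design in the original intervention group as a measure of sustainability". The Trial Summary lists sustainability among the exploratory objectives.

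SAP 10.2.2 compares volume between arms with a count GEE that has allocated group and laboratory as factors and the practice as cluster. SAP Table 1 schedules one volume collection from the laboratory system, in 06/2019. Neither names an arm or a window for later volume, and the SAP contains no sustainability analysis. SAP 3.1 gives a six-month intervention period followed by six months of follow-up, whereas 8.8 is written around a three-month period.

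**The concern.** A series from one arm shows what happened to ordering after the intervention period. It does not show how much of that is due to the order sets. The documents themselves point to several things that could move ordering over the same months:

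- Protocol 9.8 switches off the compulsory indication prompt after the intervention period, exactly where the one-arm series begins. Section 5.1 shows that the prompt applies in both arms.
- The first part of the financial incentive (9.8) is paid when appropriateness data collection ends, which is about the same time.
- Physicians are moving from paper to electronic ordering (sections 4 and 5.1), and 9.7 leaves paper orders out of the analysis.
- Ordering rules change over time. The note to Protocol Table 2 records one such rule, for amylase and lipase.
- A three-month study period cannot match the seasons of the nine months after it.

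At stake is whether persistence or fading of the volume effect can be attributed to the intervention, when the randomised controls needed for that are still unexposed for most of the window.

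**Working it through.** The documents give no sample size or power for volume or sustainability, so there is no planned figure to reproduce. The check is of the calendar, of how a time trend enters, and of what the comparison could offer.

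**Calendar, protocol (300 physicians).** Protocol 6.1 sets the measurement period: "Three months are sufficient to measure the effect of our intervention".
- Cross-over: 3 + 6 = month 9, which agrees with the nine unexposed months in 6.1.
- Window requested in 8.8: from month 3 to 3 + 9 = month 12.
- Part of that window with unexposed controls: months 3 to 9, so 6/9 = 67%. In months 9 to 12 both arms have the intervention.

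**Calendar, SAP.** With a six-month intervention period (SAP 3.1; Protocol 9.6 also says six months), the rule in 8.9.2 puts cross-over at 6 + 6 = month 12. Controls are unexposed for six further months on either timetable, but the three-month and nine-month windows in 8.8 no longer fit.

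**How a trend enters.** Let B be usual volume, R the intervention/control ratio, and d a proportional fall common to both arms between the study period and follow-up.
- One-arm change = [B × R(follow-up) × (1 − d)] / [B × R(study)] = (1 − d) × R(follow-up)/R(study).
- Concurrent ratio = [B × R(follow-up) × (1 − d)] / [B × (1 − d)] = R(follow-up).

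The hypothesised reduction is 20% (Protocol 3.2.2), so R(study) = 0.80. The size of d is an assumption, because the documents give none.

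| Assumed d | Share of the 20% effect | One-arm change if effect fully lasts | One-arm change if effect fully fades |
|---|---|---|---|
| 0% | 0 | 1.00 | 1/0.80 = 1.25 |
| 5% | 5/20 = one quarter | 0.95 | 0.95 × 1.25 = 1.19 |
| 10% | 10/20 = one half | 0.90 | 0.90 × 1.25 = 1.13 |
| 20% | 20/20 = all | 0.80 | 0.80 × 1.25 = 1.00 |

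In the last row a complete fade shows no change in the one-arm series, so it looks like full persistence. The concurrent ratio would be 0.80 if the effect lasts and 1.00 if it fades, whatever the value of d.

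**What the comparison could offer.** At 15 patients per week (Protocol 9.1) over 26 weeks, the control arm would generate 150 × 15 × 26 = 58,500 panels in those six months, or 58,500 × 0.70 = 40,950 at 70% electronic use. Between-practice variation in volume is not given. Assuming a coefficient of variation (CV) of practice means from 0.2 to 0.5, power for a 20% reduction at two-sided 5% is Φ(0.20/(CV × √(2/k)) − 1.96), with k practices per arm:
- k = 124/2 = 62 (Protocol 4): from about 100% down to 60.5%.
- k = 72/2 = 36 (SAP 3.2, assuming an even split): from 98.9% down to 39.6%.

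The comparison would be useful over much of that range, but it is not guaranteed to be precise.

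**The case against.** The strongest reply is that the plan already contains what is asked for. Protocol Table 1 commits to both arms, section 3.3.2.2 plans volume by arm, the SAP volume model needs both arms, and the 06/2019 collection in SAP Table 1 is not limited to one arm. Sustainability is also exploratory and openly described as observational in the original intervention group, so a one-arm series answers the descriptive question that was set.

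Much of this stands, and it rules out two stronger readings. A reader might infer that the trial throws away its randomised comparison. The documents do not support that: the comparison is lost only if 8.8 is followed over Table 1. A reader might also infer that the sustainability aim cannot be answered. It can be described; what is missing under 8.8 is attribution to the intervention.

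The conflict itself remains. Protocol 6 and 6.2 tie the observational design to the time after cross-over, and the reasons in 8.9.2 are reasons for cross-over, not for leaving out controls before it. Only 8.8 carries one-arm data back into the controlled months. The SAP names no arm or window that would settle it.

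Two practical objections also have force. The SAP cites a protocol version dated 07/08/2019, after the planned 06/2019 collection, so the extract may already exist. And no document states what an extract costs, so the change cannot be called free.

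**Conclusion.** The concern holds as a cheap improvement. Section 8.8 and Table 1 contradict each other on which arm supplies later volume. Under 8.8 the sustainability result cannot be separated from time trends; under Table 1 a concurrent randomised comparison covers six of the nine months requested. A common drift of 5% to 20%, which is assumed, would be one quarter to all of the hypothesised effect.

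It would go too far to say that controls remove the problem throughout. Drift cancels only before cross-over, and only so far as it is common to both arms. Removing the prompt may not be common: in the intervention arm, entering an indication also brings up the order set. In that case the comparison estimates the effect that persists without the prompt, which is still a sustainability question.

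The primary outcome, the diagnostic-error test and the study-period volume comparison are not affected.

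**What to change.** 1. Reconcile Protocol 8.8 with Table 1 by requesting total volume for both arms over the whole follow-up, by month, so that it can be cut at cross-over.
2. Restate the windows in 8.8 to fit the SAP's six-month intervention period, and give the cross-over date in both documents.
3. Add to the SAP an exploratory analysis of volume from the end of the intervention period to cross-over, as an intervention/control ratio with 95% confidence interval from the 10.2.2 model.
4. Report months after cross-over separately, labelled uncontrolled and descriptive.

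If the 06/2019 extract has already been taken, first check whether it holds the control arm. If it does, only the SAP text changes; if not, a supplementary extract is needed. The cost is control-arm records from the same laboratory systems, with no new patients or visits. The documents do not price the extract.
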